10.4.2 Analysis Methods

10.4.2.1 Summary Statistics

Summary statistics will be used for the primary outcome clinical benefit rate as well as the response rate. Clinical benefit rate is defined as the proportion of subjects with complete response or partial response or stable disease. Response rate is defined as the proportion of subjects with complete response or partial response. 95% exact confidence intervals will be provided. Kaplan-Meier product limit survival plots will be generated and median survival time and associated 95% CI will be estimated, the PFS percentage at 12 and 24 weeks will be calculated. Descriptive statistics will be used to summarize the safety data such as the DLT for both hematologic and non-hematologic toxicity per type and grade, as well as all collected AE data, which will be listed per patient, and cycle. For the biopsy samples, exploratory analyses such as multivariable logistic regression, linear regressions and survival analyses will be required to attempt to classify protein, gene, or TUNEL markers associated with clinical outcomes such as response, clinical benefit and PFS as predictive (of therapeutic impact) or prognostic (of intrinsic tumor

biology). Bio-informatics tools such as unsupervised pathway analysis will also be explored. The following molecular characteristics at baseline will be explored among others: 1) Nuclear to cytoplasmic localization of AR staining. 2) Strength of AR signaling as measured by the expression of downstream AR-regulated genes, which should reflect dependence of the tumor cell on AR function. 3) AR:ER ratio with resistance to anti-estrogen therapy.

The same summary statistics will be used for the response rate and clinical benefit rate. Response rate is defined as the proportion of subjects with complete response or partial response. Clinical benefit rate is defined as the proportion of subjects with complete response or partial response or stable disease. Kaplan-Meier product limit survival plots will be generated and median survival time and associated 95% CI will be estimated for each arm. Combined and separate data for patients with AR+ and AR- BC and those with one prior endocrine therapy and those with more than one prior endocrine therapy for metastatic breast cancer.

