Objectives	
Primary Objective: To determine the clinical benefit rate (complete and partial response plus stable disease for 24 weeks) of the combination of enzalutamide/fulvestrant.
 
Secondary Objectives:
 
1. To confirm the safety profile of the combination.2. Response rate (complete and partial response) at 24 weeks, Progression-free survival (PFS) and % of patients remaining free from progression at 12 and 24 weeks.3. To obtain serial biopsies of breast cancer pretreatment, during treatment and at time of tumor progression in order to determine the extent of AR expression and signaling in breast tissue, to evaluate the effect of enzalutamide on the tumor, and to evaluate the relationship of these effects on clinical outcomes.
Endpoints	
Primary Endpoint: Clinical benefit rate at 24 weeks
 
Secondary Endpoints: Safety, PFS, PFS12, PFS24, ORR
 
Exploratory Endpoint: Tissue studies

Subject Population	
Clinical Indication: ER+ Her2- breast cancer
 
Gender: Female
 
Age Range: 18-100 years

Trial Type	Interventional
Type of control	Non-randomized
Description of Study Agents	
Fulvestrant: 500mg given IM on days 1, 15, and 28, and then every 4 weeks as per standard of care (SOC)
 
Enzalutamide: 160mg given PO daily

Trial Blinding	Open-label
Treatment Groups	Single arm

Number of trial subjects	24 evaluable; up to 45 may be consented to allow for screen failures
Estimated enrollment period	24 months
Duration of Participation	Until disease progression or unacceptable drug-related toxicity

SCHEMATIC OF STUDY DESIGN

LIST OF ABBREVIATIONS

ACRONYM	DESCRIPTION
AE	adverse event
ALT	alanine aminotransferase
ANC	absolute neutrophil count
AR	androgen receptor
ASCO	American Society for Clinical Oncology
AST	aspartate aminotransferase
AUC	area under the curve
BC	breast cancer
CBC	complete blood count
CBR	clinical benefit rate
CFR	Code of Federal Regulations
cGCP	current good clinical practice

COMIRB 16-1001**Version Date 08-27-2019****PI: [name]**

CI	confidence interval
CLIA	Clinical Laboratory Improvement Amendments
CNS	central nervous system
CRF	case report form
CRPC	castration-resistant prostate cancer
CT	computed tomography
CTC	circulating tumor cell
CTCAE	Common Terminology Criteria for Adverse Events
CV	coefficient variation
DHT	dihydrotestosterone
DLT	dose-limiting toxicity
DSM	data and safety monitoring
DSMC	Data and Safety Monitoring Committee

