2.2 Primary Objective

To determine the clinical benefit rate (complete and partial response plus stable disease for 24 weeks) of the combination of enzalutamide/fulvestrant.

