10.1 Clinical Data

Age, ethnicity, race, gender, breast cancer histology (ductal, lobular, other), breast cancer subtype (ER, PR, Her2, Ki67, AR), detailed prior treatment history, selected comorbidities (especially insulin, metformin use), clinical response, CBR, PFS at 12 weeks, TTP. Details of treatment, including AE, SAE, and compliance.

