10.2 Sample Size

10.2.1 Determination of Sample Size

The primary outcome is the clinical benefit rate. Assuming the undesirable rate of 10% and desirable rate of 30%, a sample size of 24 provides 89% power to detect this 25% rate difference using an exact binomial test with a one-sided alpha of 0.085. If 5 or more patients show clinical benefit the drug combination warrants further evaluation. During treatment period, patients might withdraw due to toxicity or loss to follow-up before on treatment for 24 weeks. Table below summarize the statistical power and the decision rule for sample size from 24 to 20, a 20% loss in the total sample size, which is the upper bound for loss seen in practice.

Statistical Power	n	Actual Alpha	Reject H0 If R ≥
0.89	24	0.085	5
0.86	23	0.073	5
0.84	22	0.062	5
0.80	21	0.052	5
0.76	20	0.043	5

R is the response as the clinical benefit

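### Section 10.4 defines clinical benefit without the 24-week duration for stable disease that the primary objective requires; applied literally, it cannot lower, and may raise, the count against the rule of 5 or more out of 24

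*Combined protocol and SAP*

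**What the plan says.** **Objective and endpoint.** The synopsis lists the primary endpoint as "Clinical benefit rate at 24 weeks". The synopsis and section 2.2 state the objective as "clinical benefit rate (complete and partial response plus stable disease for 24 weeks", so stable disease qualifies only with that duration.

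**Analysis section.** Section 10.4.2.1 opens with "Summary statistics will be used for the primary outcome clinical benefit rate as well as the response rate" and follows directly with "Clinical benefit rate is defined as the proportion of subjects with complete response or partial response or stable disease". The same definition comes again later in 10.4.2.1 and once in 10.4.2.2. None of the three has a duration, a time point or a reference to section 2.2.

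**Rest of section 10.** Section 10.4.2.1 does give time points for progression-free survival ("the PFS percentage at 12 and 24 weeks will be calculated") but none for clinical benefit. Section 10.1 lists the data items as "clinical response, CBR, PFS at 12 weeks, TTP", again with no time point for the clinical benefit rate. The decision rule in 10.2.1 reads "If 5 or more patients show clinical benefit the drug combination warrants further evaluation". That section comes nearest to the 24-week horizon when it explains its allowance for loss: "patients might withdraw due to toxicity or loss to follow-up before on treatment for 24 weeks".

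**The concern.** The document holds two worded definitions of the quantity that drives the only formal decision in the trial. One requires 24 weeks of stable disease and the other, read literally, does not. The section an analyst would program from contains only the second, and the decision rule does not say which of the two it uses.

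The threshold is low, 5 patients out of 24, so one or two patients classified differently can change the conclusion. If short stable disease were counted, the error would favour declaring that the combination warrants further evaluation. The 10% and 30% rates in 10.2.1 would also no longer describe what is being counted, if they are 24-week rates.

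**Working it through.** **1. Reproduce the plan's figures.** Inputs from 10.2.1: n = 24, undesirable rate 10%, desirable rate 30%, pass if R is 5 or more, one-sided exact binomial test. With X ~ Binomial(24, p), the chance of passing is P(X ≥ 5) = 1 − [P(0) + P(1) + P(2) + P(3) + P(4)].

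At p = 0.10 the terms are:

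- P(0) = 0.9^24 = 0.0798
- P(1) = 24 × 0.1 × 0.9^23 = 0.2127
- P(2) = 276 × 0.1^2 × 0.9^22 = 0.2718
- P(3) = 2024 × 0.1^3 × 0.9^21 = 0.2215
- P(4) = 10626 × 0.1^4 × 0.9^20 = 0.1292

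The unrounded terms sum to 0.9149, so P(X ≥ 5) = 0.0851. The plan states 0.085. At p = 0.30, P(X ≥ 5) = 0.889; the plan states 0.89. The other four rows of the table (n = 23 to 20) also reproduce. The plan's calculation is sound for whatever quantity R stands for.

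**2. Compare the two counts on the same patients.** Let A be the patients with complete response, partial response, or stable disease for 24 weeks. Let B be those with complete response, partial response, or stable disease of any duration. Everyone in A is in B, so the count of B is at least the count of A. The two are equal if no patient's only benefit is stable disease shorter than 24 weeks; otherwise B is larger by the number of such patients.

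**3. Can such patients arise under the schedule?** Section 6.1 has imaging at week 9 and then every 8 weeks up to week 49, so the next scans fall at about weeks 17 and 25. A patient stable at week 9 who has progressed by week 17 is in B but not in A. This example requires reading 10.4 as counting stable disease of any duration.

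**4. Illustrate the size.** The documents give no rate of short stable disease. Assume that the 10% in 10.2.1 is a 24-week rate, that the true rate equals it, and that k further patients among the 24 have only short stable disease and are counted. The rule is then met when X ≥ 5 − k.

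| Short-stable patients counted (k) | Condition on X | Chance of passing, n = 24, p = 0.10 |
|---|---|---|
| 0 (as planned) | X ≥ 5 | 0.085 |
| 1 | X ≥ 4 | 0.0851 + 0.1292 = 0.214 |
| 2 | X ≥ 3 | 0.2143 + 0.2215 = 0.436 |

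**The case against.** The best reply is that the endpoint is already fixed. The synopsis and section 2.2 define it with 24 weeks. Section 10.4.2.1 calls it the primary outcome, which points to that endpoint, and 10.2.1 treats leaving before 24 weeks as a loss of sample. There is also good evidence of shorthand. Section 2.3 places the response rate at 24 weeks, and 10.4 drops that time point too. Section 10.4 also refers to each arm in a single-arm trial, which suggests text carried over from elsewhere. On this view an analyst would have to override the stated primary endpoint to go wrong.

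Much of this stands. A reader might infer that 10.4 deliberately changes the endpoint to stable disease at any time, or that a patient stable only at week 9 certainly counts. The documents do not support either inference: 10.4 does not say at any time or as best response, and read together with the synopsis endpoint its list could mean status at 24 weeks. The missing time point in 10.1 is also weak evidence, since that section is only a list of data items.

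The reply does not remove the conflict. The words in 10.4 are framed as a definition and appear three times, and nothing in section 10 states the duration or sends the reader to section 2.2. The mention of 24 weeks in 10.2.1 implies a horizon without defining what counts.

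**Conclusion.** The inconsistency is real and should be corrected, although it may be no more than shorthand. On a literal, duration-free reading of 10.4, the count set against 5 out of 24 cannot be lower than under the objective. It is higher whenever a patient's only benefit is stable disease shorter than 24 weeks. On the reading that carries 24 weeks over from the synopsis and section 2.2, nothing changes.

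The size cannot be taken from the documents. The values 0.21 and 0.44 show how sensitive the rule is to one or two reclassified patients, given a true 24-week rate of 10%. A reader might take them as the trial's actual false-positive rate. They are not: they rest on an assumed number of short-stable patients and on treating the 10% in 10.2.1 as a 24-week rate, which that section implies but does not state. The planned alpha of 0.085 and power of 0.89 are correct for the endpoint as the objective defines it.

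**What to change.** - In both places in 10.4.2.1 and the one in 10.4.2.2, add the objective's duration to the definition, so that it ends with stable disease *for 24 weeks*, and label the quantity as the clinical benefit rate at 24 weeks.
- In 10.2.1, add one sentence saying that R in the rule of 5 or more is counted with this definition.

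The cost is wording only: three words and a label at three places, plus one sentence. The planned n, threshold, alpha and power stay as they are, and no visit or scan is added. The one downside is that the reported rate may be lower than under the duration-free wording. How to classify patients who have no 24-week assessment is a separate question that this change does not settle.

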10.4 Research (Statistical) Methods

Data collected in this study will be presented using summary tables, patient data listings, and figures. Disease evaluations will be performed by investigators per the RECIST ___ criteria. Each enrolled patients will provide tumor tissues at baseline (0 week) and during treatment (4 weeks) and at disease progression. 24 pre- and treatment- biopsy pairs are planned for this study. Patients lacking pre- or treatment- biopsies will be replaced.

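### Multivariable logistic models of clinical benefit are planned with about 5 to 7 expected events and no limit on covariates, penalisation or internal validation, so multi-marker fits could look discriminating by chance

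*Combined protocol and SAP*

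**What the plan says.** For the biopsy samples, Section 10.4.2.1 of the combined protocol and SAP plans "exploratory analyses such as multivariable logistic regression, linear regressions and survival analyses". It treats these as necessary for sorting tissue markers (protein, gene and TUNEL) into predictive and prognostic ones, with response, clinical benefit and PFS as the outcomes. A later sentence in that section names three baseline characteristics for exploration, and leaves the list open: AR localisation, strength of AR signalling and the AR:ER ratio. Section 10.3 lists 13 laboratory items, including RNA sequencing, exome sequencing and proteomics.

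The data available to these models follow from two other places. Section 10.4 says "24 pre- and treatment- biopsy pairs are planned for this study". Section 10.2.1 gives the planning rates, "Assuming the undesirable rate of 10% and desirable rate of 30%, a sample size of 24 provides 89% power", and the decision rule: "If 5 or more patients show clinical benefit the drug combination warrants further evaluation".

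Section 10.2.2 declines to adjust type I error for multiple biomarkers. The marker power statements, in Sections 1.4 and 10.2.2, concern two-group t-tests of non-responders against responders. No section states a number of covariates per model, a penalised method, a way of handling separation, or any cross-validation or bootstrap correction.

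**The concern.** In logistic regression, the smaller of the two outcome groups limits how many coefficients can be estimated usefully. With about 5 to 7 patients showing benefit, three markers in one model have about two events each. Response (complete plus partial) is a subset of clinical benefit, so it has no more events.

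An unpenalised model fitted that thinly follows noise: its apparent performance in the same 24 patients exceeds its performance in new ones, and its likelihood-ratio test rejects too often. What is at stake is the choice of candidate markers. Section 7.2 expects a set of putative biomarkers, and Section 1.3.1 sends the promising ones on to further work. A marker combination that fits well by chance would use up that effort.

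**Working it through.** **Inputs.** n = 24, null rate 10%, target 30%, go rule of at least 5 (Section 10.2.1); 24 biopsy pairs (Section 10.4). The number of markers per model, k, is not in the plan. Every value of k below is an assumption, as is the number of markers screened.

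**The plan's own figure.** Section 10.2.1 specifies "using an exact binomial test with a one-sided alpha of 0.085". P(X ≥ 5) for a binomial with n = 24 is 0.0851 at 10% and 0.8889 at 30%, which matches the printed 0.085 and 0.89. The rows for n = 23 to 20 also reproduce.

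**Expected benefit events.** 24 × 0.30 = 7.2 at the target and 24 × 0.10 = 2.4 at the null rate. If n falls to 20, the target gives 20 × 0.30 = 6.0. The range of 5 to 7 is therefore derived from the go threshold and the target; the plan does not state it. At a true 30%, the 90% range of the count is 4 to 11.

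**Events per marker.** Three markers: 5/3 = 1.7 to 7/3 = 2.3. Five markers: 5/5 = 1.0 to 7/5 = 1.4.

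**Simulation.** n = 24 with the event count fixed; k independent standard-normal markers unrelated to outcome; unpenalised maximum-likelihood logistic regression; 1,500 runs per cell. Entries are for 5 / 6 / 7 events.

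| k | Mean apparent AUC | AUC at least 0.8 | Likelihood-ratio rejection at nominal 5% | Complete separation |
|---|---|---|---|---|
| 1 | 0.615 / 0.608 / 0.605 | 3% / 3% / 2% | 5.1% / 6.9% / 6.4% | 0 / 0 / 0 |
| 2 | 0.68 / 0.67 / 0.67 | 13% / 8% / 9% | 7.7% / 7.7% / 9.9% | 0 / 0.1% / 0 |
| 3 | 0.73 / 0.72 / 0.71 | 28% / 20% / 14% | 11.2% / 8.5% / 8.1% | 0.4% / 0.2% / 0 |
| 5 | 0.81 / 0.80 / 0.78 | 55% / 47% / 39% | 15.3% / 13.9% / 12.9% | 5.6% / 2.1% / 1.0% |

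Mean AUC in new data is 0.50 in every row. The three-marker rejection rate averages (11.2 + 8.5 + 8.1)/3 = 9.3%. A separate simulation of the same kind gave about 9% with 3 markers and 14% to 17% with 5.

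**Sensitivity.**
- With 12 events, the largest possible size for the smaller outcome group, mean noise AUC is still 0.69 with 3 markers and 0.76 with 5.
- If the best 3 of 10 noise markers are chosen by univariate AUC before fitting, mean apparent AUC is 0.85 (5 events) and 0.82 (7 events). For the best 3 of 20 it is 0.90 and 0.87.

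**The case against.** The strongest reply is that the plan does not specify the model criticised here. Multivariable logistic regression is one item in an illustrative list, and no covariate count is given. A reader might infer that the three baseline characteristics go into one model, but they appear in a separate sentence as things to explore. One marker plus one clinical covariate is also multivariable. This stands: the multi-marker results show what an open plan permits, not what it commits to.

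A reader might also infer that the models will break down through separation. With 3 markers that is negligible (0.4% of runs or fewer). It reaches about 1% to 6% with 5 and becomes common only in larger models (20% to 41% with 8), and neither size has a source in the documents.

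The plan proposes no AUC and no patient-level score. In Section 10.4.2.1, classifying refers to labelling markers as predictive or prognostic. AUC serves here as a measure of overfitting; the likelihood-ratio rejection rate makes the same point about the significance of a fitted model. Inflation of odds ratios is not quantified here.

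A single noise marker already shows about 0.61, because the fit chooses its direction. The excess from 3 markers is therefore about 0.10 to 0.12 (0.707 − 0.605 and 0.732 − 0.615), not the full distance from 0.50.

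The event count could also be higher. Section 10.4.2.1 defines clinical benefit without the 24-week condition in Section 2.2, and Section 10.2.2 considers a 50% response rate. Even so, the smaller outcome group cannot exceed 12, and the optimism persists there.

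Finally, the work is exploratory. PFS is already a marker outcome (Sections 1.3.1, 2.4 and 10.4.2.1), and Section 1.3.1 requires biological plausibility, preclinical comparison and confirmation with other assays. These safeguards limit the consequence, but none of them corrects the fit in these 24 patients.

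**Conclusion.** The concern holds in a limited form. The plan names multivariable logistic regression for outcomes with about 5 to 7 expected events, and nothing in it restrains the size of the model or corrects its apparent performance. If 3 markers are entered together, optimism is moderate: mean noise AUC of 0.71 to 0.73 and about 9% rejection at nominal 5%. With 5 it is marked: 0.78 to 0.81 and about 13% to 17%. Screening before fitting makes it worse.

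These sizes rest on assumed marker counts, independent normal noise markers, and an event count inferred from the planning rates. The documents do not support saying that the fitted models will mislead, only that they could. The effect is confined to the choice of candidate markers; the primary endpoint and the go rule are untouched. This is a minor, inexpensive improvement.

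**What to change.** In Section 10.4.2.1, state that:

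- marker models for binary outcomes use Firth-penalised logistic regression with one marker and at most one clinical covariate, in line with the single-marker comparisons powered in Sections 1.4 and 10.2.2;
- any multi-marker model uses ridge or lasso, and only cross-validated or bootstrap-corrected performance is reported, with any marker screening repeated inside each resample;
- the PFS analyses of markers are kept as planned, with a 4-week landmark for on-treatment change markers, because PFS runs from the first day of enzalutamide (Section 10.5.2.3) and the change is known only after the second biopsy.

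The cost is wording and analysis code; no patients, visits or assays are added. The downside is that no jointly adjusted multi-marker odds ratios would be reported, but 24 patients cannot support them reliably.

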1.4 Hypothesis

Enzalutamide with fulvestrant, by blocking both AR and ER signaling, will synergize in patients with ER+ AR+ metastatic breast cancer. It may prevent AR from taking over from ER when ER signaling is blocked. The extent of AR expression that correlates with enzalutamide efficacy is unknown and is an objective of this study; therefore, all patients, including those with “AR-negative” breast cancer (although this is expected to be fewer than 10%), will be enrolled to receive standard of care fulvestrant with enzalutamide. We hypothesize that 1) AR localization (a shift from nuclear to cytoplasmic) when comparing the pretreatment to the ~4 week tissues will represent a pharmacodynamics (PD) marker of enzalutamide activity. In tumors that respond to treatment, we would not only expect such a shift in AR localization, but also 2) a reduced expression in AR-regulated genes as well as subsequent changes in downstream processes. Thus, comparison of pre- vs during treatment tissues should allow us to identify PD markers as well as predictive biomarkers that indicate no response to enzalutamide (such as no

change in Ki67 or TUNEL). We will be able to measure Ki67 using standard IHC assays as well as a quantitative measurement by Reverse Phase Protein Microarray (RPMA). Multivariate analysis will be required to attempt to classify protein, gene, or TUNEL markers associated with PFS as predictive (of therapeutic impact), prognostic (of intrinsic tumor biology), or mixed as discussed above. A similar plan to compare the preclinical with the clinical analyses should facilitate the discovery and validation of putative biomarkers. The evaluation of Ki67 and TUNEL will provide the preliminary data necessary to mount our preoperative trial proposed in Years 3-5. Sample size and power consideration: 24 baseline samples will provide 80% power to detect a mean difference in change (baseline-during treatment) of 1 (or 1.3) standard deviation between the two groups (NR vs R) using one-sided 2-group t-test with a significance level of 0.05, assuming the response is 50% (or 20%). Statistical analysis plan: the same analysis approaches described in aim 1 will be used here, with the changes (baseline –during treatment) instead of the baseline values. Coefficient variation (CV) will be calculated for each potential biomarkers and biomarkers with smaller CV will be particularly interesting.

2. OBJECTIVES AND OUTCOMES:

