2.3 Secondary Objectives

1. To confirm the safety profile of the combination.
2. Response rate (complete and partial response) at 24 weeks, Progression-free survival (PFS) and % of patients remaining free from progression at 12 and 24 weeks.
3. To obtain serial biopsies of breast cancer pretreatment, during treatment and at time of tumor progression in order to determine the extent of AR expression and signaling in breast tissue, to evaluate the effect of enzalutamide on the tumor, and to evaluate the relationship of these effects on clinical outcomes.

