3.1 Study Design

[figure not shown]
Single arm, non-randomized, open-label treatment consisting of:

- Fulvestrant 500 mg IM given days 1, 15, 28, then every 4 weeks as per standard of care (SOC). Fulvestrant may have already been started.
- Enzalutamide 160 mg daily.

If pre- or perimenopausal, patients will also receive goserelin 3.6 mg sq every 4 weeks (or equivalent) as per standard of care (SOC).

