4.1 Inclusion Criteria

1. ER+ Her2- breast cancer
2. Metastatic
3. Female, at least 18 years of age
4. Candidate for fulvestrant therapy – patients who have started fulvestrant may enter this trial if within 3 months of starting fulvestrant
5. Measurable or evaluable by RECIST 1.1

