6. ECOG PS 0-2
7. Able to swallow study drug and comply with study requirements
8. Tumor available for fresh biopsy (two biopsies – pretreatment as regards enzalutamide, and during treatment at 4 weeks). The patient will be also be asked if they would be willing to provide a third biopsy at time of progression.
9. If patient is pre- or peri- menopausal, then will need to have concurrent ovarian suppression. Patients may have already gotten the loading dose of ovarian suppression. Pre- or peri- menopausal subjects must have a negative urine pregnancy test confirmed at screening.
10. ANC >1000/uL and platelets >75,000/uL at screening visit
11. Total bilirubin < 1.5 times upper limit of normal (ULN) at the screening visit unless an alternate nonmalignant etiology exists (eg, Gilbert's disease)
12. Aspartate aminotransferase (AST) or alanine aminotransferase (ALT) < 3 times ULN or < 5 times ULN if patient has documented liver metastases
13. Creatinine < 1.5 times ULN
14. INR < 1.5 times ULN, or if on warfarin, can safely transition off for biopsy
15. Willing to donate blood for research at 4 time points
16. Written informed consent obtained prior to biopsies and blood samples
17. Agreement to exercise appropriate use of contraception. Subjects should use 2 acceptable methods of birth control (one of which must include a condom as a barrier method of contraception) starting at the time of screening for an enzalutamide study and continuing throughout the course of treatment and for at least three months after enzalutamide is discontinued.

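### With every patient on both drugs in one arm, markers cannot be sorted into predictive, prognostic or mixed, and a paired change in Ki67, TUNEL or ER signaling cannot be credited to enzalutamide alone

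*Combined protocol and SAP*

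**What the plan says.** **Classification.** Section 10.4.2.1 plans multivariable logistic, linear and survival models that will "attempt to classify protein, gene, or TUNEL markers associated with clinical outcomes such as response, clinical benefit and PFS as predictive (of therapeutic impact", or as prognostic. Section 1.4 states the same aim with a third class: multivariate analysis is to "classify protein, gene, or TUNEL markers associated with PFS as predictive (of therapeutic impact), prognostic (of intrinsic tumor biology), or mixed". It also expects the comparison of tissue before and during treatment to "identify PD markers as well as predictive biomarkers that indicate no response to enzalutamide", giving absence of change in Ki67 or TUNEL as the example.

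**Design.** Section 3.1 describes "Single arm, non-randomized, open-label treatment consisting of" fulvestrant and enzalutamide. Sections 1.4 and 7.3 confirm that all patients, whatever their AR status, receive both drugs. No fulvestrant-alone group or external control is planned.

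**Timing of fulvestrant.** Section 3.1 notes: "Fulvestrant may have already been started". Section 4.1 adds that "patients who have started fulvestrant may enter this trial if within 3 months of starting fulvestrant". The two required biopsies are "pretreatment as regards enzalutamide, and during treatment at 4 weeks" (section 4.1, item 8), so the first may be taken before fulvestrant, during loading, or after it.

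**Attribution.** Section 2.3, item 3, gives as purposes of the serial biopsies "to evaluate the effect of enzalutamide on the tumor, and to evaluate the relationship of these effects on clinical outcomes". Section 6.3.2 reads the week-4 biopsy differently: both drugs are at steady state by then, and the sample shows the subacute effects of the treatment on AR and ER signaling.

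**The concern.** A predictive marker is one whose relation to outcome differs with and without the drug. A prognostic marker relates to outcome whichever treatment is given. Telling them apart needs patients who did not get enzalutamide, and this trial has none.

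The paired biopsies have a related gap. Section 5.2 says fulvestrant itself blocks and degrades ER and inhibits estrogen signaling. In a patient who starts both drugs on day 1, the change to week 4 is the effect of the pair. In a patient already past fulvestrant loading it is closer to the effect of adding enzalutamide, though still without a control. The plan pools these patients and does not name fulvestrant timing as a subgroup or covariate.

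What is at stake is what gets reported and carried forward. A marker of slow-growing disease could be published as predicting benefit from enzalutamide, or a Ki67 fall caused by starting fulvestrant could be reported as an enzalutamide effect. Section 1.4 intends the Ki67 and TUNEL results as preliminary data for a later preoperative trial.

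**Working it through.** **1. The plan's own figures.** Section 10.2.1 (n = 24, 5 or more with benefit, 10% against 30%) reproduces: exact binomial alpha 0.0851, power 0.889. For the change in markers between the no-response group (NR) and the others (R), section 1.4 states 80% power at 1 SD (50% response) or 1.3 SD (20% response), one-sided 0.05. The noncentral t gives 80% power at 1.048 SD (12 vs 12) and 1.290 SD (5 vs 19), which match after rounding. These calculations compare outcome groups within the one arm. None concerns a treatment contrast or a marker-by-treatment interaction.

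**2. Can the classes be separated?** Model: outcome = a + b·marker + c·treatment + g·(marker × treatment). Prognostic means b ≠ 0 and g = 0; predictive means g ≠ 0. With treatment = 1 for everyone, the treatment column equals the intercept column and the interaction column equals the marker column. The design matrix has rank 2 of 4, and only b + g can be estimated. With two randomized arms the rank would be 4.

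Illustration with assumed rates, half the patients marker-positive. On the combination, clinical benefit is 40% (marker-positive) and 20% (marker-negative), 30% overall, which is the plan's desirable rate. The observed difference is 20 points.

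| Assumed benefit on fulvestrant alone (positive / negative) | Prognostic part | Interaction | Class |
|---|---|---|---|
| 40% / 20% | 20 points | (40 − 40) − (20 − 20) = 0 | prognostic |
| 30% / 20% | 10 points | (40 − 30) − (20 − 20) = 10 points | mixed |
| 20% / 20% | 0 | (40 − 20) − (20 − 20) = 20 points | predictive |

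The trial's data are the same in all three rows. More patients or more covariates in the same arm do not change this.

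**3. How far can the paired change be off?** Assumptions, since the documents give no figures: additive effects; fulvestrant alone moves the marker by d = 0.5 to 1 SD; a share q of patients is already at full fulvestrant effect at the first biopsy. Then mean change = enzalutamide's added part + (1 − q)d.

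| d | q = 75% | q = 25% |
|---|---|---|
| 0.5 SD | 0.125 SD | 0.375 SD |
| 1 SD | 0.25 SD | 0.75 SD |

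The excess is zero if d = 0. That may hold for AR localization, because sections 1.2 and 1.3 tie blocked nuclear translocation of AR to enzalutamide.

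**4. The NR-vs-R change test.** The two group means shift apart by (difference in share already started) × d. If timing is balanced, the shift is zero and the error stays at 5%. Simulated one-sided error, 12 vs 12, with an assumed 25-point imbalance:

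| Direction of imbalance | d = 0.5 SD | d = 1 SD |
|---|---|---|
| in the direction tested | 8.8% | 13.7% |
| reversed | 2.6% | 1.5% |

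Adjusting for one binary covariate (fulvestrant already started or not) returns the error to about 5%. If fulvestrant does not move the marker, the covariate lowers power from 80% to 78% with balanced timing and to 75–76% at a 25-point imbalance.

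**The case against.** **The work is exploratory.** The synopsis lists tissue studies as an exploratory endpoint, section 10.4.2.1 only speaks of an attempt, section 10.2.2 leaves multiple markers unadjusted for that reason, and section 1.3.1 calls the markers putative and wants them confirmed. This stands as a limit on the consequence. It excuses imprecision, but not a label that the data cannot support.

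**Preclinical work will sort it out.** Sections 1.3.1 and 1.4 plan to set clinical tissue beside preclinical models and to confirm candidates with better assays. That adds plausibility and better measurement. It does not supply patients treated without enzalutamide.

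**The plan already reads the biopsy as a combination effect.** Section 6.3.2 does. The attribution problem is therefore partly one of inconsistent wording, with section 2.3 out of line.

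**Stronger readings that the documents do not support.**
- A reader might infer that no change in Ki67 or TUNEL cannot be taken as no response to enzalutamide. If effects are additive and the two drugs do not push the marker in opposite directions, no change on both drugs implies no added enzalutamide change. In that sentence only the word predictive is open to objection.
- A reader might infer that the NR-vs-R test is biased. That needs fulvestrant timing to differ between the groups, which the documents do not address. The error could then rise or fall.
- A reader might extend the criticism to the Ki67 hypothesis in section 2.4. It links the Ki67 fall to response to therapy and to PFS, without crediting enzalutamide.

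**Conclusion.** The predictive, prognostic or mixed classification in sections 10.4.2.1 and 1.4 cannot be made from this trial. This is a failure of identifiability, so it holds at any sample size and rests on no assumed figure. What can be estimated is association with outcome on the combination.

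Attributing the paired change to enzalutamide, as section 2.3 implies, is not supported for Ki67, TUNEL and ER-signaling markers. The size, 0.125 to 0.75 SD over the ranges shown, rests on assumed values for fulvestrant's own effect and for the share already started. The concern is weaker for AR localization.

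The effect on the NR-vs-R test is a conditional illustration, not a demonstrated fault. A reader might also infer that the trial's main conclusion is in doubt. It is not: the rule of 5 or more in section 10.2.1 judges the combination and is untouched. The consequence is confined to secondary and exploratory tissue claims, but the correction is cheap and should be made.

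**What to change.** (a) In sections 10.4.2.1 and 1.4, replace the predictive/prognostic/mixed classification with *associated with outcome on the combination*. In the section 1.4 sentence on no response to enzalutamide, drop the word *predictive*.

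(b) In section 2.3, describe the paired change as the effect of the combination, consistent with section 6.3.2. The AR-localization hypothesis in section 1.4 can stay as a hypothesis about enzalutamide.

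(c) Use the fulvestrant start date to report paired changes by status at first biopsy (naive or already started). Add that one binary covariate to the NR-vs-R change analysis as a sensitivity analysis.

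**Cost.** Wording, one table and one extra model. The start date should be obtainable from the detailed prior treatment history listed in section 10.1. The claim becomes more modest. Subgroup sizes are unknown and may be small: the 95% half-width for a mean change, t(0.975, n − 1)/√n, is about 1.05 SD at n = 6 and 0.64 SD at n = 12. The adjusted analysis gives up about 2 to 5 points of power if fulvestrant does not move the marker.
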